10.5.2 Physical Examinations, Vital Signs, ECG Parameters and Clinical Laboratory Test Values

By-subject listings of physical examinations, vital signs, ECG parameters and clinical laboratory data will include indications of values that are outside the reference ranges, and values that are clinically significant. Observed and change from baseline (Screening/Visit 1) values for vital signs, ECGs, and clinical laboratory test results will be summarized as appropriate by treatment arm and dose. Shift tables describing out-of-reference range shifts will be provided for vital signs, ECGs and clinical laboratory test results from the **Screening/Visit 1** to **EoS/Visit 6**, as appropriate by treatment arm and dose.

10.5.3 C-SSRS

By-subject listings of any suicidal ideation or behavior will be listed.

10.6 Efficacy Analyses

This is an open-label study with no control group. Efficacy data will be summarized using descriptive statistics. The proportion of attacks treated with lasmiditan 100 mg and with lasmiditan 200 mg which respond at 2 hours will be calculated for each 3 month period.

10.6.1 Headache Response

Headache pain free at 2 hours will be defined as a reduction in headache severity from moderate (2) or severe (3) at baseline to none (0) two hours after dosing with study drug. MBS free at 2 hours will be defined as a 'no' response to the presence of the symptom (either nausea, phonophobia, or photophobia) that was identified as MBS at predose, 2 hours after dosing with study drug.

A qualifying migraine is defined as a migraine treated with study drug within 4 hours of onset

Subjects taking rescue medication within the first two hours or who fail to record headache severity at 2 hours will be assumed to be non-responders in the mITT and the ITT analyses.

A subject is defined to have used rescue medication within the first two hours post dosing if at least one medication is documented in the rescue medication log in the subject electronic diary for which:

$0 \text{ (min)} < \text{date/ time rescue medication (diary)} - \text{date/ time of dosing (diary)} < 120 \text{ (min)}$.

Subjects who do not provide a headache pain severity rating at baseline or who use other medication prior to the study drug for the study migraine attack will be assumed to be non-responders for the mITT and ITT analysis.

10.6.2 Sensitivity Analyses of the Primary and Key Secondary Endpoints

The analyses of pain free at 2 hours and of MBS free at 2 hours are defined as proportions. The prespecified approach for handling missing data is to assume that subjects with missing data are nonresponders. While this approach is appropriately conservative, a sensitivity analysis will be incorporated to exclude subjects with missing data.

10.6.3 Other Efficacy Analyses

10.6.3.1 Headache relief

The proportion of attacks treated with study medication with headache relief (moderate or severe headache at baseline, which became mild or none, or mild headache which became none) at 2 hours post dose will be evaluated. The time course to headache relief will be explored up to 48 hours.

10.6.3.2 Headache recurrence

The proportion of attacks treated with study medication with headache recurrence (moderate or severe headache at baseline, which became pain free at 2 hours post-dose and worsened again up to 48 hours post-dose) will be evaluated based on first dose.

10.6.3.3 Headache rescue

The requirement for rescue medication at 2 hours and between 2 and 24 hours and 24- 48 hours (yes or no) will be evaluated based on first dose. The information on rescue medication use will be presented descriptively by time of use and treatment arm.

10.6.3.4 Associated Symptoms of Migraine

Descriptive analysis of the associated symptoms of migraine, nausea, phonophobia and photophobia, will be performed at 2 hours. Freedom from each symptom will be defined as a 'no' response to the presence of the symptom 2 hours after dosing with study drug. Summary statistics will be presented by treatment arm and timepoint as appropriate.

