5.5.2 Treatment

Subjects will be allowed to treat all acute migraine attacks with study drug. Study migraines should be of moderate or severe intensity that is not improving. The attack is to be treated within

4 hours of onset. Subjects should not exceed a total dose of 200 mg of lasmiditan in a 24-hour period.

- **Prior to dosing the subject will record:**
 - Time of onset
 - Time migraine pain becomes moderate or severe and the severity ((2) moderate or (3) severe) of the pain.
 - Presence or absence (yes or no) of each of the following associated symptoms of migraine: nausea, phonophobia and photophobia.
 - From the list of associated symptoms **present** the subject will identify which **ONE** is most bothersome to them as the MBS.
 - Presence or absence (yes or no) of vomiting.
 - Degree of interference with normal activities
- **Subject will dose with study drug and record time of dosing.**
- Subject will record their response to treatment for 48 hours after dosing with study drug. Total time to record response is up to 72 hours if a second dose of study drug is taken for recurrence of migraine (for subjects randomized to lasmiditan 100 mg) (See Section 9.1.8).
- Subjects will report any unusual symptoms not felt before with a migraine during each migraine treated with study drug as well as any concomitant medication use by way of the e-diary. Sites will receive an alert and should contact the subject within 48 hours to discuss the unusual symptoms and determine if the symptom(s) are an AE along with the duration and effect of the AE on the subject.

5.5.3 Month 1/Visit 2

This visit is to occur at approximately the same time of day (\pm 1 hour), 30 days (\pm 2d) from **Screening/Visit 1**. The following assessments will be performed:

- Collect empty dosing card and/or any unused study drug and review dosing compliance.
- Review patient diary compliance.
- Collect resource utilization (See Section 9.1.1.3).
- Have subject complete MIDAS questionnaire (See Section 9.1.1.2 and Appendix 2).
- Obtain C-SSRS (See Section 9.1.6 and Appendix 3).
- Assess for AEs and use of concomitant medications.
- Perform a brief symptom-related physical examination if indicated by an AE (See Section 9.1.2.).
- Obtain vital sign readings (See Section 9.1.3).

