### **5.1 Changes and Clarifications from the Planned Analysis**

The protocol detailed mITT-2nd Dose and PP-2nd Dose populations. However, the decision was made to run efficacy analyses on the ITT and mITT populations. The populations such as safety-2nd, mITT-2nd Dose and PP-2nd Dose populations were therefore removed. Additionally PP population was removed, as primary endpoint of this study is safety.

The analyses of the primary efficacy measure and other related measures described in the protocol were limited to headaches that were of moderate or severe intensity at the time of dosing. In keeping with subsequent input to CoLucid from the Food & Drug Administration (FDA), the efficacy endpoints will take into account headaches that were of mild intensity at the time of treatment.

The protocol mentioned sensitivity analysis for efficacy endpoints for missing diary data. It was decided not to conduct this analysis, as primary endpoint of this study is safety. The complications of missing efficacy diary data were tested in parent study.

The protocol does not mention an additional subgroup analysis but subgroup analyses described in Section 11.8 will be provided.

Though the protocol did not specify this, it was decided that exploratory analyses would be repeated separately for relief of each associated symptom of headache, including vomiting.

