#### **11.2.1.2 Most Bothersome Symptom Free (MBS-Free)**

MBS-free is defined as the absence of the associated symptom of migraine (either nausea, phonophobia, or photophobia) at 2-hour post-dose that was identified pre-dose as the most bothersome symptom. Subjects who record that no symptoms were present at baseline will be excluded from the key MBS analyses.

Subjects who do not provide a symptom rating at baseline will be excluded from the analysis except following possibility:

- Subjects who record at least one symptom present at baseline, but who do not designate one as most bothersome, will be treated as if all symptoms present are most bothersome and will be considered MBS-free at any time point post-dose only if all symptoms present at baseline are no longer present at that time point.

Subjects taking rescue medication within the first two hours, or who fail to record a symptom rating at 2 hours, will be assumed to have not achieved MBS-free.

The counts and percentages of which symptom was chosen as the most bothersome symptom will also be presented by treated migraine attack.

Subjects missing symptoms at baseline or at the summarized time point will not be summarized at that time point.

These analyses will be presented by treatment group, for the ITT and mITT populations, based on first dose and for ITT2nd dose rescue and recurrence population based on second dose. These presentations will be summarized on ITT and mITT migraine level analysis.

The endpoint of MBS-free will be summarized at the 0.5, 1, 2, 4, 24, and 48-hour post-dose time points. This summary will be repeated separately for each symptom (nausea, phonophobia, and photophobia) on the mITT and ITT population at treated migraine level.

This data will be summarized for the 1st, 2nd, 3rd, 4th, 5th, 10th, 15th, and 20th treated migraine.

For subjects that treated 5 or more migraines, MBS-free at 2 hours will be summarized across the first five treated migraines and as overall response for all treated migraines. Overall response for each subject in this subgroup is calculated by dividing the number of successful responses (responses at 2 hours) by total number of attacks treated.

Additionally, a time to MBS Free Kaplan-Meier analysis will be conducted on the first treated migraine for the subject-level ITT population by dose.

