#### **11.2.1.5 Presence of Migraine Symptoms**

Counts and percentages of the presence of associated symptoms will be presented at the 0.5, 1, 2, 4, 24, and 48-hour post-dose time points. These will be summarized by treatment group for the ITT population and ITT-2nd dose rescue and recurrence populations based on second dose at treated migraine level for each treated migraine attack.

The presence of the following associated symptoms will be presented based on the response to the presence of that symptom at that time point.

- Nausea
- Phonophobia
- Photophobia
- Vomiting

This data will be summarized overall and for the 1st, 2nd, 3rd, 4th, 5th, 10th, 15th, and 20th treated migraine.

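### Freedom from each associated symptom is defined without requiring the symptom before dosing, and the SAP does not clearly supply that condition

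*Protocol*

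**What the plan says.** Protocol 10.6.3.4 deals with nausea, phonophobia and photophobia one by one. Its rule is: "Freedom from each symptom will be defined as a 'no' response to the presence of the symptom 2 hours after dosing with study drug". Nothing in that section refers to the answer given before dosing.

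The comparable definitions do look back to baseline. MBS-free in Protocol 10.6.1 concerns the symptom "that was identified as MBS at predose, 2 hours after dosing with study drug". Headache relief in Protocol 10.6.3.1 means "moderate or severe headache at baseline, which became mild or none, or mild headache which became none". SAP 11.1, 11.2.1.1 and 11.2.1.6 keep a baseline condition for the pain outcomes.

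The pre-dose status needed for the same condition is collected. Protocol 5.5.2 has the subject record "Presence or absence (yes or no) of each of the following associated symptoms of migraine: nausea, phonophobia and photophobia", and vomiting is recorded before dosing as well.

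The SAP touches individual symptoms in three places:

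- Section 5.1 says that "exploratory analyses would be repeated separately for relief of each associated symptom of headache, including vomiting". It does not define relief.
- Section 11.2.1.5 covers nausea, phonophobia, photophobia and vomiting at six post-dose times: "The presence of the following associated symptoms will be presented based on the response to the presence of that symptom at that time point". It sets no restriction on baseline status.
- Section 11.2.1.2 states, for the MBS: "Subjects who record that no symptoms were present at baseline will be excluded from the key MBS analyses". It then says the MBS-free summary will be repeated for nausea, phonophobia and photophobia, without saying which attacks form the denominator.

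**The concern.** A rate called freedom will be read as the share of attacks in which the drug cleared the symptom. Under the protocol rule it also contains attacks in which there was nothing to clear, so it depends on how common the symptom was at Hour 0 as well as on what happened after the dose. An attack with new nausea after dosing is also pooled with one whose nausea persisted.

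There is no placebo arm against which a reader could judge the level of the rate. If symptom freedom or relief is reported on this definition, it will look better than resolution of existing symptoms, by an amount that differs between symptoms with their baseline prevalence.

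**Working it through.** The documents state no figure for this outcome, so there is nothing to reproduce. The check is algebra with assumed inputs.

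**Quantities (none given in the documents)**

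- q: share of treated attacks with the symptom at Hour 0
- r: share of those attacks with a 'no' at 2 h (true resolution)
- e: share of attacks without the symptom at Hour 0 that have it at 2 h (new onset)

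**Rate under Protocol 10.6.3.4**

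Defined rate = q·r + (1-q)(1-e)

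Excess over resolution = q·r + (1-q)(1-e) - r = (1-q)(1-e-r)

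The excess is zero when q = 1 and positive whenever e + r is below 1.

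**Illustration with r = 0.40, e = 0.05**

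| q | q·r | (1-q)(1-e) | Defined rate | Excess over 0.40 |
|---|---|---|---|---|
| 0.4 | 0.16 | 0.57 | 0.73 | 33 points |
| 0.6 | 0.24 | 0.38 | 0.62 | 22 points |
| 0.8 | 0.32 | 0.19 | 0.51 | 11 points |
| 0.9 | 0.36 | 0.095 | 0.455 | 5.5 points |

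Over q from 0.3 to 0.9, r from 0.3 to 0.6 and e from 0 to 0.2, the excess runs from 0.1 × (1 - 0.2 - 0.6) = 2 points to 0.7 × (1 - 0 - 0.3) = 49 points.

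**Comparison of the two doses.** If q and e are the same in both arms, the difference in defined rates is q times the difference in r. A true 10-point difference becomes 4, 6 or 8 points at q = 0.4, 0.6 or 0.8. The definition dilutes the contrast.

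**Can baseline and 2-hour prevalence be compared instead?** SAP 8.5 tabulates baseline symptoms and SAP 11.2.1.5 gives presence at 2 h. Two marginal rates give only net change. Suppose nausea is present in 40% of attacks at Hour 0 and 25% at 2 h:

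- 37.5% resolution with no new onset: 0.40 × 0.625 = 0.25
- 60% resolution with 15% new onset: 0.40 × 0.40 + 0.60 × 0.15 = 0.16 + 0.09 = 0.25

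Both fit the same two tables. Only a within-attack cross-classification separates them.

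**The case against.** The best reply is that the SAP governs the analysis and its per-symptom table does not score freedom at all. Section 11.2.1.5 is headed as presence and reports counts and percentages of presence, for which all attacks are a proper denominator. This stands. A reader might infer that the SAP will publish inflated relief rates; the documents do not say so. Overstatement arises only if the complement of that table, or the protocol definition itself, is reported as relief.

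Second, the by-symptom repeat of the MBS-free summary in 11.2.1.2 may already be conditional, because the MBS is chosen from symptoms present before dosing. That is a natural reading but not the only one. The denominator could be attacks where that symptom was the MBS, attacks where it was present, or all attacks. Vomiting is not in the list, although 5.1 promises relief analyses that include it.

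Third, baseline prevalence is tabulated in SAP 8.5, so a high rate of absence at 2 h need not be read blind. This helps, but it shows net change only.

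Three stronger readings are tempting and should not be drawn:

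- *The freedom rate mostly measures baseline absence.* That depends on q. At q = 80%, r = 50% and no new onset, the rate is 60%, of which 40 points are resolution and 20 are absence at baseline.
- *Vomiting freedom would be close to 100% whatever the drug does.* Protocol 10.6.3.4 does not cover vomiting; Protocol 10.6.3.5 summarises its presence only. No document gives its prevalence.
- *New nausea or vomiting would be lost as a safety signal.* SAP 12.1 bears on relatedness and still presents those events by treatment group. Under Protocol 9.2.1 the diary asks about anything unusual not felt with a migraine before and alerts the site. Adverse event capture does not depend on this efficacy table.

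**Conclusion.** The point holds in limited form. Protocol 10.6.3.4 omits the baseline-presence condition that its neighbours carry, and followed literally it exceeds true resolution by (1-q)(1-e-r). The direction is upward as long as e + r is below 1. The size is unknown, because q, r and e are not in the documents; the 2 to 49 points above reflect the assumed ranges only.

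No SAP section clearly supplies the condition. The presence table is sound as prevalence and does not measure relief, the by-symptom repeat leaves its denominator open and omits vomiting, and the relief named in 5.1 has no definition.

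The consequence is modest. These are descriptive additional summaries in a study whose primary endpoint is safety and whose secondary endpoint is headache response. With balanced arms the definition would shrink a difference between doses; it would not create one.

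**What to change.** - In SAP 5.1, define relief of (freedom from) each associated symptom at 2 h as a 'no' at 2 h among treated attacks with that symptom recorded as present at Hour 0, and note that this replaces the definition in Protocol 10.6.3.4.
- Apply that denominator to the by-symptom repeat in SAP 11.2.1.2, and extend it to vomiting.
- State how a missing 2-hour symptom answer is counted. Section 11.2.1.2 contains both a rule that counts it as failure and a rule that leaves it out.
- Keep the table in SAP 11.2.1.5 as prevalence. Add a shift table of Hour 0 by 2 h for each symptom, with new onset among attacks without the symptom at Hour 0 shown separately. SAP 11.2.1.7 already plans a table of this form for disability.

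The cost is SAP wording and a re-tabulation of diary data already collected. The denominators will be smaller, especially for vomiting, so counts should be shown beside the percentages.

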10.6.3.5 Additional analyses

Summary statistics will be presented on presence of vomiting, disability (4 point scale: not at all (0), mild interference (1), moderate interference (2), completely, needs bed rest (3)), and patient global impression of change (7 point scale) by treatment arm and timepoint as appropriate.

10.7 Analysis of Second dose

10.7.1 Analysis of second dose for rescue

A second dose of study drug will be considered rescue medication if taken by a subject that did not achieve headache pain free at 2 hours and completed the 2 hour assessments prior to taking the second dose.

Summary statistics will be presented by treatment arm on relief of migraine symptoms (pain free and MBS free) along with the time course to headache relief explored up to 48 hours. Subjects that use an alternative rescue medication will not be included in the summary statistics of response to treatment for rescue.

10.7.2 Analysis of second dose for recurrence

A second dose of study drug will be considered treatment for recurrence if taken by a subject that achieved headache pain free at 2 hours, completed the 2 hour assessments, and then experienced documented recurrence of mild, moderate, or severe migraine pain prior to taking the second dose.

Summary statistics will be presented by treatment arm on the relief of migraine symptoms (pain free and MBS free) along with the time course to headache relief explored up to 48 hours. Only subjects that used a second dose of study drug for recurrence of migraine will be included in the summary statistics of response to treatment for recurrence.

10.8 Resource Utilization

By-subject listings of any resource utilization will be listed and will be summarized using descriptive statistics, separated by treatment arm and visit. Days missed from work and/or school or daily activities will be tabulated from information recorded on the MIDAS scale separated by treatment arm and visit.

11. DIRECT ACCESS TO SOURCE DATA/DOCUMENTS

11.1. Study Monitoring

The investigator will allow the Sponsor or a designee:

- to inspect the site, the facilities, and the material used for the study;
- to meet all members of the team involved in the study;
- to consult all the documents relevant to the study;
- to check that the eCRFs have been correctly completed;
- to have direct access to source documents for comparison of data therein with the data in the eCRFs;
- to check that AEs have been documented; and
- to verify that the study is carried out in compliance with the protocol.

This study will be monitored at regular intervals, by agreement of the Investigator. All information dealt with during these visits will be treated as strictly confidential.

The Investigator will provide the sponsor with the following:

- Progress reports at regular intervals
- Adequately completed eCRFs

11.2 Data collection

Investigational sites will be supplied with instructions on accessing the web-based Electronic Data Capture (EDC) system via secure web portal. Representatives of Lilly (or designee) will train designated site staff on the EDC system. Investigational site staff will not be given access to the EDC system until the required training is completed and documented. Designated site staff will enter the data required by the protocol into the electronic CRFs. Automatic validation programs check for data discrepancies in the CRFs and, by generating appropriate error messages, allow modification or verification of the entered data by the site staff. After database lock, the Investigator will receive a CD or DVD of the subject data for archiving at the investigational site.

11.3 Audits and Inspections

The Investigator will be informed that an audit will be carried out, at the request of the Sponsor, before, during, or after the study.

The Investigator will be informed that the Regulatory Agencies may also carry out an inspection. In this case, the Investigator must inform the sponsor as soon as he receives the notification of inspection.

The Investigator must allow the representatives of the Regulatory Agencies and persons responsible for the audit:

- to inspect the site, facilities, and material used for the study;
- meet all members of his team involved in the study;
- have direct access to study data and source documents; and
- to consult all the documents relevant to the study.

12. QUALITY CONTROL AND QUALITY ASSURANCE

The Investigator or the appointed persons agree to complete the subject's eCRFs, at each investigation. Only the Investigator or appointed persons in his/her team may fill out or correct the eCRFs. The eCRFs will display the subject number corresponding to the order of inclusion in the study (7 digits) and the initials of the subject (1 letter for forename, 1 letter for middle name and 1 letter for surname).

The Sponsor or their designee will review the eCRFs entered by investigational site staff for completeness and accuracy and instruct the investigational site staff to make any required corrections or additions. Queries will be sent to the investigational site using an electronic data query within the EDC system. Designated investigational site staff will be required to respond to the query and make any necessary changes to the data.

All corrections and alterations of data on the eCRFs must be made by the Investigator or by the appointed persons as instructed in the eCRF guidelines. If corrections or alterations are required of paper source documents, corrections may be made in the following manner: strike through the datum to be corrected using a single line so that the original remains legible; correction fluid must never be used. The correction should be written to the side or above the original entry and must be initialed and dated by the Investigator or one of his designated team.

It is the responsibility of the monitor to make certain that all data are completed on the eCRFs. The Investigator and the monitor must sign and date the eCRF per the eCRF procedure in order to attest respectively to the:

- authenticity of the data collected in the eCRF, and
- coherence between the data in the eCRF and those in the source documents.

Concomitant medications entered into the database will be coded using the WHO Drug Reference List, which employs the Anatomical Therapeutic Chemical classification system. Adverse events and medical history will be coded using the Medical dictionary for regulatory activities (MedDRA) terminology.

ECGs will be evaluated for safety through central readers and the results will be sent electronically to the study database. Clinical laboratory samples will be processed through a central laboratory and the results will be sent electronically to the study database.

Randomization codes and data about all study drugs dispensed to the subject will be tracked using a centralized randomization process. The system will be supplied by a vendor, who will also manage the database. The database will be sent electronically to the study database (or a designated CRO).

After the above actions have been completed and the database has been declared to be complete and accurate, it will be locked for data analysis. Any changes to the database after that time can only be made with the approval of Lilly.

At the end of the study, the Investigator will receive a CD or DVD of all data submitted for subjects at that site. This CD or DVD will serve as the archival copy and must be retained per the record retention policy.

The Investigator will keep a log of volunteers screened for study participation as appropriate and will indicate the reason why individual volunteers did not enter the study. The log will be submitted to the CRO or their designee as defined in the study manual. The Investigator must submit to the Sponsor or its representatives a completed eCRF for each subject who receives any study drug.

If computerized medical files are used, and if the computer system allows, no change made in the medical files by the Investigator should obscure the original information. The record must clearly indicate that a change was made and clearly provide a means to locate and read the prior information. The Investigator will save data at regular intervals.

The Investigator must guarantee the safety of the study data in the medical files by implementing security measures to prevent unauthorized access to the data and to the computer system.

